Open-label Prospective Randomized Study to
Determine the Efficacy and Safety of Two Dosing
Regimens of ACTHar in the Treatment of Proliferative
Lupus Nephritis

NCT02226341

January 3, 2024

Study Title**ACTHar in the treatment of Lupus Nephritis**

Principal Investigator: *[name] [name]*

Institution and department: *CUMC, Rheumatology*

A. SPECIFIC AIM

Start with a concise summary of the overall project (a few sentences). Please include hypotheses for each endpoint (see Section C) and provide rationale in Section B.

Open-label prospective randomized study to determine the efficacy and safety of two dosing regimens of ACTHar in the treatment of proliferative lupus nephritis. The treatment of lupus nephritis (LN) has remained mostly unchanged for many decades: High doses of steroids are still the cornerstone of LN therapy despite their devastating side effects. It is only recently that attempts at changing the requirements regarding steroid use have been made. The current proposal will evaluate the role of ACTH in the form of ACTHar gel in the treatment of proliferative LN. While we expect that a part of the therapeutic effects of ACTHar in LN will be mediated through the endogenous production of steroids, we hypothesize that a larger portion of the ACTH benefit may be due to the direct anti-inflammatory and reno-protective effect of ACTH dependent on the activation of the melanocortin receptors, rather than steroid production.

Accordingly, we propose that this study will evaluate the most effective dose of ACTHar gel in proliferative LN (Class III and IV) that produces the least steroid-like side effects, comparing two doses of ACTHar in conjunction with Mycophenolate Mofetil (MMF); MMF, in conjunction with Prednisone, is considered the current standard of care for LN. The dose of ACTHar was inferred based on the positive results of a study of membranous nephropathy. The primary outcome is renal response. Secondary outcomes are overall lupus activity and steroid side effects.

B. BACKGROUND AND CLINICAL SIGNIFICANCE**Introduction**

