Further understanding of the role of ACTH in kidney disease is provided by a recent study by Bombback in patients with refractory nephrotic syndrome despite appropriate immunosuppression. ACTH was effective in inducing remission. Twenty-one patients with nephrotic syndrome were treated with ACTH 80 mg SQ twice a week: 11 with idiopathic membranous nephropathy, 4 with membranoproliferative glomerulonephritis, 1 with focal segmental glomerulosclerosis, 1 with minimal change disease, 1 with immunoglobulin A (IgA) nephropathy, 1 with Class V systemic lupus erythematosus (SLE) glomerulonephritis, 1 with monoclonal diffuse proliferative glomerulonephritis, and 1 with unbiopsied nephrotic syndrome. Eleven out of 21 patients (52%) achieved a complete or partial remission, with 4 (19%) in complete remission. Five patients reported steroid-like adverse effects (2 weight gain, 2 hyperglycemia, 1 bone demineralization), but there were no severe infections [30].

The mechanism of action of Acthar in the treatment of SLE is currently being investigated. H.P. Acthar Gel and endogenous ACTH stimulate the adrenal cortex to secrete cortisol, corticosterone, aldosterone, and a number of weakly androgenic substances by binding to MC2R. The trophic effects of endogenous ACTH on the adrenal cortex are not well understood beyond the fact that they appear to be mediated by cAMP. Prolonged administration of large doses of Acthar induces hyperplasia and hypertrophy of the adrenal cortex. The release of endogenous ACTH is under the influence of the nervous system via the regulatory hormone released from the hypothalamus and by a negative corticosteroid feedback mechanism. Elevated plasma cortisol suppresses pituitary ACTH release. Acthar binding to melanocortin receptors in a variety of cell types, including immune cells, is likely responsible for some of the beneficial effects.

Recent data from Multiple Sclerosis (MS) suggests the ACTHar gel (80 IU X3 daily doses) is superior to 1000 mg of IV Medrol given monthly for 12 months in the treatment of MS exacerbations [31], raising the possibility of improved outcomes in LN with ACTHar in a manner similar to that described by Gourley: the addition of Medrol to the standard of care for LN improved outcomes [8].

Urinary Biomarkers

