Recurrent renal flares cause renal damage leading to glomerulosclerosis and irreversible deterioration of renal function [9]. Safe and effective maintenance therapies are needed to prevent renal relapses, reduce progression to ESRD, and reduce the chance of adverse events. Clinical trials focusing on maintenance therapies by Contreras *et al.* [13], ALMS (Aspreva Lupus Management Study) [26] and Houssiau *et al.* (MAINTAIN) [27] suggest that MMF is at least equivalent to AZA for maintenance therapy. A summary of the maintenance trials is presented in **Table 3**. The current study patients will be maintained on MMF for total treatment duration of 2 years.

Non-immunomodulatory treatments are also used in the treatment of LN patients. These include ACE inhibitors, ARBs, and statins and are not restricted in this study.

C. RESEARCH DESIGN AND METHODS

Study Design

The study is a randomized, controlled phase IV, single center trial of ACTHar plus CellCept (Mycophenolate Mofetil), as defined by the ASPREVA Nephritis Trial (MMF 3000 mg daily) in the treatment of lupus nephritis. The primary outcome will be assessed at 6 months. Thereafter, subsequent therapy will be with CellCept maintenance 2000 mg daily.

Study Duration

Follow-ups for each patient will be conducted for a total of 24 months.

Primary Outcome

The proportion of participants who achieve a complete response at 6 months.

1. Complete response (CR) is defined as *all* of the following criteria having been achieved:
 - a. Stabilization of estimated glomerular filtration rate (i.e., a 6-month eGFR level \pm 10% of baseline) or improvement if the screening value is changed from patient's baseline
 - b. Inactive urinary sediment (red blood cells per high-power field [RBCs/HPF] <5-10, not due to gyn bleeding)
 - c. Urine protein/creatinine ratio <0.5

Secondary Outcomes

1. Frequency of responders = CR + Partial Responders (PR). PR = improvement from baseline of at least \geq 50% in all abnormal renal parameters (proteinuria and serum creatinine) without deterioration of any measurements at 6 months
2. Frequency of extra-renal flares as defined by the SELENA-SLEDAI Flare Index. Extra-renal disease activity measured by SELENA-SLEDAI and BILAG
3. Steroid -like side effects: increased in BP by 20 mmHg for both SBP and DBP, increased blood sugar with a fasting plasma glucose level \geq 126 mg/dl, weight gain \geq 10% of the initial weight, infections
4. Side effects

Inclusion Criteria

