Clinical response data will be evaluated every 3 months and reported as overall percent responders and complete and partial responders in each dosing arm. Also, side effects (including steroid-like side effects) will be evaluated every 3 months and reported to the IRB and Questcor. The observed response rates in this study will be compared to the historical expected complete response rate in LN of 20%, and total renal responses of 50%. A two-sided chi-square test will be used to compare the proportion of subjects with complete response and total responses between the treatment arms and these expected values. Differences in the baseline characteristic between the two treatment groups will be evaluated using descriptive statistics, the two-sample t-test for continuous variables and the chi-square test for categorical variables. Times to event for the endpoints of partial and complete remission will be analyzed with the use of the Cox proportional-hazards model. The proportion of SAEs in the study regimen will be compared with the expected SAEs from other lupus nephritis studies using a two-sided chi-square test at the 0.05 level of significance without using continuity correction.

The research will be conducted as per CUMC's strict guidelines, thus preventing unauthorized collection, use, and/or disclosure of data. Strict physical, technical, and administrative safeguards to protect data from unauthorized access and/or tampering will be in place. Appropriate measures to ensure confidentiality will be employed. The aggregate data will be entered in a database. The data will be kept in locked facilities that can only be accessed by study investigators or a member of the research team. This will be for a period of up to 10 years, after which the data collection forms and database from this study will be destroyed.

Sample Size Justification *Include power analyses or justification for enrollment plan*

N=10 patients per dosing arm.

References

2. Lam G, Petri, M: Assessment of systemic lupus erythematosus. *Clin Exp Rheumatol* 2005, 23:S120-S132.

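### Steroid-like side effects are part of the dose comparison, but weight, blood pressure and fasting glucose are kept only as threshold events and no between-arm analysis of them is planned on any scale

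*Combined protocol and SAP*

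**What the plan says.** Section A (Specific Aim) says the study will "evaluate the most effective dose of ACTHar gel in proliferative LN (Class III and IV) that produces the least steroid-like side effects", by comparing two regimens on an MMF background.

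Section C, Secondary Outcomes, item 3 gives the only definition of steroid-like side effects. Blood pressure counts if "increased in BP by 20 mmHg for both SBP and DBP". The rest of the item reads "increased blood sugar with a fasting plasma glucose level \geq 126 mg/dl, weight gain \geq 10% of the initial weight, infections". Three of the four components are therefore measurements reduced to yes/no; infections are events by nature. The item does not say whether components are analysed singly or as one composite.

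The Statistical/Analytical Plan says that "side effects (including steroid-like side effects) will be evaluated every 3 months and reported to the IRB and Questcor". The comparison that it describes between the arms covers complete and total renal response. SAEs are compared with rates from other studies "using a two-sided chi-square test at the 0.05 level of significance without using continuity correction". T-tests are named only for baseline characteristics. The Sample Size Justification is "N=10 patients per dosing arm", with no effect size, SD or power.

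On background rates, the Rationale for ACTH reports 21 patients with nephrotic syndrome treated twice weekly: "Five patients reported steroid-like adverse effects (2 weight gain, 2 hyperglycemia, 1 bone demineralization), but there were no severe infections".

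**The concern.** The aim needs a contrast between the two regimens on side effects, and the plan gives no route to one. The outcome is scored as events and then reported. If the cited rates carry over, about one patient per arm would have the event for weight (10 × 2/21 = 0.95), and the same for glucose. Counts that small can hardly separate the regimens. A report of similar side effects on both doses could then reflect the scale of the outcome rather than the drug, although the underlying measurements might carry more information.

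**Working it through.** There is no planned power or effect size to reproduce, so this compares two ways of analysing one component.

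**Inputs from the documents.** 10 per arm; low-dose event rate p0 = 2/21 = 9.5% (cited cohort, event definitions not given). Two-sided 0.05 and no continuity correction are borrowed from the SAE comparison, because nothing is stated for steroid-like effects.

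**Assumptions.** Normally distributed change, equal SD in both arms, no dropout, and a true shift of d SD in the every-other-day arm.

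**Threshold scale.** The higher-dose event rate is p1 = Φ(z(p0) + d). For d = 1: Φ(−1.309 + 1) = Φ(−0.309) = 37.9%. Power is the summed probability of all significant 10 v 10 tables.

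**Measured scale.** Two-sample t-test, 18 df, critical value 2.101, noncentrality d√(10/2). For d = 1 this is 2.236, and power is 56%.

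| Shift (SD) | p1 | Chi-square | Fisher | t-test | Loss, 1 − chi-square/t |
|---|---|---|---|---|---|
| 0.5 | 21% | 6% | 2% | 19% | 70% |
| 0.8 | 31% | 16% | 6% | 40% | 60% |
| 1.0 | 38% | 27% | 13% | 56% | 53% |
| 1.5 | 58% | 63% | 44% | 89% | 29% |

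**Range.** The largest chi-square loss is at p0 = 5% and d = 0.5: 1 − 0.017/0.185 = 91%. The smallest is at p0 = 20% and d = 1.5: 1 − 0.708/0.887 = 20%.

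**Sparse counts.** The chance of no event in the twice-weekly arm is (19/21)^10 = 37%. Even then the other arm needs 4 of 10 events by chi-square (p = 0.025) or 5 of 10 by Fisher (p = 0.033).

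**Composite event.** Suppose a patient counts if any of the three measured components crosses its cut-off, each with p0 = 2/21 and each shifted by 1 SD. With independent components the rates are 1 − (19/21)^3 = 25.9% and 1 − (1 − 0.379)^3 = 76.0%, and chi-square power is 62%. With correlation 0.3 the rates are 23.2% and 68.1%, power 52%. With correlation 0.5 they are 20.9% and 62.6%, power 46%. A single continuous measure has 56%. At 0.8 SD the composite has 43%, 34% and 30%, against 40%. Like for like, the mean of the three standardised changes (simulated, correlation 0.3, 10% rate per component) has 83% at 1 SD, against 52% for the composite event.

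**Precision on the measured scale.** Without baseline adjustment, the 95% half-width for a difference is 2.101 × √(2/10) = 0.94 SD.

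**The case against.** The strongest objection is that no planned power is lost: the plan contains no between-arm test of steroid-like effects, so the threshold test in the table is a construct. This stands. The first gap is the missing comparison, and the scale comes second.

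A reader might infer that the trial throws away about half its power on side effects. The documents do not support that as a fixed figure. It needs a 10% event rate and a shift near 1 SD, and neither is stated. The cited cohort had mixed glomerular diseases and reported effects without cut-offs. Item 3 may also be meant as one composite, which at 1 SD performs about as well as weight alone.

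Two further points stand. Under Treatment Description the every-other-day arm moves to twice weekly after month 1, so the arms share a regimen in months 2 and 3. A 1 SD difference may be optimistic, and a contrast at month 3 alone would come after the regimens converge. Also, patients with toxicity may have ACTHar reduced or stopped (Study Drug Discontinuation), and blood pressure is treated to a target (Prophylactic Medications). Both can dilute a mean difference, while an event once recorded stays recorded.

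Finally, threshold events are a legitimate clinical safety summary, and this is one of four secondary items behind a renal primary outcome. That argues for keeping the counts, not against adding estimates.

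**Conclusion.** The point holds in limited form. The aim calls for a comparison of steroid-like effects between two regimens; the plan scores the measured components only as events and names no comparison on any scale. For a single component at 10 per arm, the event is less sensitive than the measured change throughout the range examined. The relative loss by uncorrected chi-square runs from about 20% to about 90% over event rates of 5-20% and shifts of 0.5-1.5 SD. These figures rest on normality, equal SDs, no dropout and an event rate taken from another population.

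It does not follow that measured values would make the side-effect aim well powered. At 0.5 SD the t-test has 19% power, and at 10 per arm it reaches 80% only for a shift of about 1.33 SD. Nor can it be said that the values are already in hand: Day-0 and follow-up fasting glucose depend on the attached schedule of assessments, which is not in the text reviewed. This is an inexpensive improvement to a secondary analysis and leaves the primary outcome untouched.

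**What to change.** Keep the threshold events and infections as counts by arm. Add to the Statistical/Analytical Plan an exploratory between-arm analysis of percent weight change, SBP, DBP and fasting glucose (log scale), each adjusted for its Day-0 value and reported as an adjusted difference with a 95% confidence interval.

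Include all randomised patients and the values recorded at study visits. Cover the visit nearest the end of month 1, while the regimens differ, as well as month 3; a repeated-measures model would do this. Do not rely on month 3 alone, or on the last value before a switch to prednisone, which would give patients unequal exposure times. Report by arm how many patients had ACTHar reduced or stopped, or had prednisone or antihypertensive treatment changed, so that dilution can be judged. State whether item 3 is read by component or as a composite.

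The cost is a paragraph in the plan and four small analyses. It needs no extra patients, and no extra measurements if the schedule already collects these values; that must be confirmed. The downside is several secondary estimates without multiplicity control, each imprecise at this size. They should be labelled exploratory and read from their intervals.

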1. Diagnosis of systemic lupus erythematosus (SLE) by American College of Rheumatology (ACR)/SLICC criteria
2. Age \geq 16 years
3. Active lupus nephritis defined by:
 - a. Kidney biopsy documentation of International Society of Nephrology/Renal Pathology Society (ISN/RPS) Class III or Class IV proliferative nephritis (including Class V occurring in combination with Class III or IV) within 12 months, and a urine protein/creatinine ratio >1 at time of entry to study
4. Ability to provide informed consent

Exclusion Criteria

1. Moderately severe anemia (Hgb < 8 mg/dL)
2. Neutropenia ($< 1,000/\text{mm}^3$)
3. Thrombocytopenia (platelets $< 50,000/\text{mm}^3$)
4. Positive purified protein derivative (PPD) test confirmed by positive Quantiferon TB gold.
5. Pulmonary fibrotic changes on chest radiograph consistent with prior healed tuberculosis
6. Active infections that in the opinion of the investigator increase the risks to the subject.
7. Known human immunodeficiency virus (HIV) and hepatitis B or C
8. End-stage renal disease (estimated GFR clearance $< 20 \text{ mL/min}/1.73 \text{ m}^2$)
9. History of cancer, except carcinoma in situ and treated basal and squamous cell carcinomas
10. Pregnancy
11. Lactation
12. Unwillingness to use a medically acceptable form of birth control (including but not limited to a diaphragm, an intrauterine device, progesterone implants or injections, oral contraceptives, the double-barrier method, or a condom)
13. Previous failure to respond to MMF
14. Use of rituximab within the past year
15. Use of experimental therapeutic agents within the past 60 days
16. Greater than or equal to 5 times the upper limit of normal of liver function tests (aspartate aminotransferase [AST], alanine aminotransferase [ALT], or alkaline phosphatase)
17. Severe, progressive, or uncontrolled renal, hepatic, hematological, gastrointestinal, pulmonary, cardiac, or neurological disease (or, in the investigator's opinion, any other concomitant medical condition that places the participant at risk by participating in this study) with the exception of diseases or conditions related to active SLE
18. Current substance abuse

Treatment Description

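### Exclusion 1 contradicts itself: the label describes moderately severe anaemia, but the haemoglobin cut-off beside it is in mg/dL and no patient can meet it

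*Combined protocol and SAP*

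**What the plan says.** The Exclusion Criteria in Section C open with three blood-count limits. Item 1 reads "Moderately severe anemia (Hgb < 8 mg/dL". Items 2 and 3 set limits for neutrophils (below 1,000 per mm³) and platelets (below 50,000 per mm³).

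Item 1 contains the only haemoglobin value in the documents. The nearest other criterion is item 17, which excludes "Severe, progressive, or uncontrolled renal, hepatic, hematological, gastrointestinal, pulmonary, cardiac, or neurological disease". Item 17 also lets the investigator exclude a patient for any other concomitant condition that puts that patient at risk. It gives no haemoglobin value, and it applies "with the exception of diseases or conditions related to active SLE".

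**The concern.** An exclusion criterion is the standard against which eligibility, and later protocol deviations, are judged. Item 1 gives two descriptions of the same patient, one in words and one in numbers, and they cannot both apply. Anyone who fits the words has a haemoglobin far above the number.

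The criterion is applied before patients start MMF at 3 g daily (Treatment Description) and before skin biopsies, which are planned for all patients at screening and at week 24 (Section B, Skin Biopsies). If the number governs, the limit never operates. Enrolling a patient with severe anaemia would then breach nothing in the numeric limit, and a monitor auditing against it would have no ground for recording a deviation.

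**Working it through.** **Inputs**

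- Printed cut-off: haemoglobin below 8 mg/dL (Exclusion Criteria, item 1).
- Conversion: 1 g = 1,000 mg.
- Patient range: the documents give none. I assume about 2 to 18 g/dL, deliberately wide.
- Planned enrolment: 10 patients in each of two arms (Treatment Description; Sample Size Justification).

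**Step 1: convert the printed cut-off.** 8 mg/dL ÷ 1,000 = 0.008 g/dL, which is 0.08 g/L.

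**Step 2: test patient values against it.** Haemoglobin in mg/dL = value in g/dL × 1,000. Ratio to the cut-off = that result ÷ 8.

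| Haemoglobin (g/dL) | In mg/dL | Ratio to cut-off | Excluded by the printed number? |
|---|---|---|---|
| 2 | 2,000 | 250 | No |
| 5 | 5,000 | 625 | No |
| 7 | 7,000 | 875 | No |
| 8 | 8,000 | 1,000 | No |
| 12 | 12,000 | 1,500 | No |
| 18 | 18,000 | 2,250 | No |

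Across the assumed range, every value lies 250 to 2,250 times above the cut-off and none is excluded. The result does not depend on the ends of that range: a patient would need a haemoglobin below 0.008 g/dL to meet the limit.

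**Step 3: see whether the unit explains the conflict.** For illustration only, if the same number were in g/dL, values of 2, 5 and 7 would be excluded and values of 8 and above would not. The criterion would then separate patients and agree in kind with its label. That is why a unit slip is the likeliest explanation, but the documents do not state the intended threshold.

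**Step 4: see whether another criterion fills the gap.** Item 17 can reach severe or uncontrolled haematological disease, so anaemia from causes other than lupus remains covered at the investigator's judgement. Inclusion criteria 1 and 3 require every participant to have SLE with active nephritis. Anaemia related to active SLE is therefore foreseeable in this population, and it is what item 17 exempts. Items 2 and 3 concern other blood counts and are stated in workable units.

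**The case against.** The strongest reply is that the criterion begins with words and the number only glosses them. On any ordinary clinical reading, a patient with a haemoglobin of 6 or 7 g/dL fits those words, and a single-centre rheumatology team enrolling 10 patients per arm would probably see the slip at once. This largely stands. It is why the point is a conflict between label and number, and why the likely effect is small. It does not remove the conflict: the words give no boundary of their own, and the only boundary printed cannot be used.

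A reader might infer something stronger, namely that the eligibility rules as a whole let every anaemic patient in. The documents do not support that. Only the numeric part of item 1 fails; its label still expresses an intent to exclude, and item 17 still covers anaemia unrelated to active SLE.

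Two routes to harm are also tempting and should not be used. One is an automated eligibility check that applies the printed unit; the documents describe no such system. The other is the risk of kidney biopsy in an anaemic patient. No kidney biopsy after entry is scheduled: inclusion criterion 3 asks for one already documented within 12 months, and the Biomarkers section uses renal tissue where it is available. The skin biopsies are the study procedure that the documents do plan for everyone.

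An error in reading the PDF is possible in principle but unlikely, because the printed unit is complete and well formed.

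**Conclusion.** The point holds as an internal contradiction in an operative entry criterion. The printed limit is 0.008 g/dL, no patient can meet it, and nothing else in the documents supplies a haemoglobin value. Taken literally, the numeric limit excludes nobody, and a deviation from it could not be identified. Item 17 covers the gap only in part.

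The importance is minor. The factor of 1,000 is the ratio of milligrams to grams and does not measure an effect on patients or results. Nothing in the documents shows that the limit was applied literally or that a severely anaemic patient was enrolled. The primary outcome definition, the sample size and the analysis are unaffected.

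The conclusion rests on the unit being printed as the authors wrote it and on the assumption that patients' haemoglobin is measured in whole grams per decilitre, with 2 to 18 g/dL as the illustrative range. That this is a unit slip is a strong inference from the label, not something the documents state.

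**What to change.** The sponsor should reconcile the label, number and unit in exclusion 1 and confirm the intended threshold. This review does not set it. Exclusion 1, and any screening document that repeats it, should then be corrected.

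Once the limit is confirmed, the recorded screening haemoglobin of every enrolled patient should be checked against it, and any patient who falls on the excluded side documented.

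The cost is one correction to the criterion and, at planned enrolment, 2 × 10 = 20 values to look up. No recalculation or change to the analysis is needed.

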The investigator will maintain adequate records of the disposition of the investigational agent, including the date and quantity of drug that was received, the participants to whom the drug was dispensed (participant by participant accounting), and an account of any drug accidentally or deliberately destroyed. Records for receipt, storage, use, and disposition of the study drug will be maintained on site. A drug-dispensing log will be kept current for each participant and will contain the identification of each participant and the date and quantity of drug dispensed. All records regarding disposition of the investigational product will be available for inspection by Questcor.

ASSESSMENT OF COMPLIANCE WITH STUDY MEDICATION

ACTH and MMF compliance will be checked at each visit.

Dosage and Administration of Acthar *Daily /weekly dose, administration, frequency*

Patients will be treated with CellCept 3 grams daily and randomly assigned to ACTHar gel 80 U biw or Acthar gel 80 U qod.

The dose of 80 U biw was chosen based on the published literature in MN [30].

In an attempt to improve outcomes, we also suggest a higher dose of 80 U qod to be used for one month of “induction”. Patients in the 80 U qod will be tapered to 80 biw after the first month of therapy.

Patients will be maintained on ACTHar for a total of 3 months.

Patients that do not achieve complete response at week 12 will be offered the option to continue ACTHar 80 U biw for a total of 6 months, or 24 weeks.

Laboratory Testing and Study Schedule --see schedule of events

Patient Monitoring and Evaluation *Contingencies for patients not responding (i.e. dose adjustment, schedule change)*

Glucocorticoids may be increased during the study for worsening renal and extra-renal manifestations of SLE. The dose may be increased as required by the clinical manifestations up to 1 mg/kg/d. ACTHar will be discontinued and patients will be considered non-responders. Renal relapses, as defined by increase in proteinuria at two consecutive visits will require discontinuation of the study regimen and treatment based on investigator preference.

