The major short-term side-effects of ACTH are salt and water retention, hypertension, hyperglycemia, central nervous system stimulation, peptic ulceration and immunosuppression. While such effects are reversible, if the use is prolonged, additional adverse effects including osteoporosis, cataracts, skin fragility, myopathy, Cushingoid facies, hirsutism, alopecia, fat re-distribution, and striae may occur, as well as infections which can be life-threatening.

Potential Pitfalls and Contingencies *Describe plans to address possible problems*

Study Drug Discontinuation

1. SLE Extra-renal Flare—severe BILAG A or SLEDAI flares
2. Renal Flare – increase proteinuria by 30% and/or increased in creatinine by 25% over the baseline visit 0, confirmed by repeat analysis. Proteinuria needs to be confirmed by a 24 hour urine P/C ratio.
3. ACTHar related steroid-like side effects – HTN, DM, hypoK refractory to optimal management
4. Severe life-threatening infections

Study drug can be decreased for ACTHar related AE, as described above. Patients will be closely monitored to document maintained efficacy. We propose the following taper regimen, 80 mg qod, decreased to 80 mg biw for one week if AE continues, decrease to 60 biw for one week, then 40 biw, and finally 20 biw.

If the study drug is discontinued for SLE related increased activity, the patients will be treated with the appropriate dose of prednisone and continued to be followed up until resolution of the symptoms. At the end of the 3 month treatment period, ACTH will be discontinued. In the event of adrenal insufficiency upon discontinuing the drug either for side effects or end of therapy, the previous dose of ACTH will be restarted and the above taper regimen will be followed.

Data Processing and Analysis

Statistical /Analytical Plan *Include data management and quality assurance*

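### The protocol gives two renal discontinuation rules that differ in criteria and apparently in what is stopped, and nothing reconciles them

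*Combined protocol and SAP*

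**What the plan says.** Two places in the combined protocol and SAP tell the investigator when to stop treatment for renal worsening.

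- **Patient Monitoring and Evaluation:** "Renal relapses, as defined by increase in proteinuria at two consecutive visits will require discontinuation of the study regimen and treatment based on investigator preference". Its preceding sentences concern a glucocorticoid increase for worsening disease. They say that ACTHar is then stopped and the patient counts as a non-responder.
- **Potential Pitfalls and Contingencies, Study Drug Discontinuation, item 2:** a renal flare is "increase proteinuria by 30% and/or increased in creatinine by 25% over the baseline visit 0, confirmed by repeat analysis". It adds: "Proteinuria needs to be confirmed by a 24 hour urine P/C ratio". A later paragraph gives prednisone when study drug is stopped for increased lupus activity.

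Other text bears on what is being stopped:

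- Study Drug Discontinuation: "Study drug can be decreased for ACTHar related AE, as described above", followed by an ACTHar step-down.
- Assessment of Compliance with Study Medication: "ACTH and MMF compliance will be checked at each visit".
- Dosage and Administration of Acthar: "Patients will be maintained on ACTHar for a total of 3 months", with an option to extend to 6 months.
- Maintenance therapies: "The current study patients will be maintained on MMF for total treatment duration of 2 years".
- Study Duration: "Follow-ups for each patient will be conducted for a total of 24 months".

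Treatment Description separately allows a switch to oral prednisone for worsening nephritis on the investigator's judgment.

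**The concern.** An investigator with a patient whose proteinuria is rising finds two instructions with different tests, different confirmation steps and different consequences. Applied literally, the looser test stops treatment in patients whom the stricter test would leave on it, while the creatinine limb of the second catches patients whom the first ignores. The wording therefore decides who comes off treatment and which drug they come off.

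It also touches the analysis. The protocol states how a patient is classified after a glucocorticoid increase. It does not state this for a patient stopped under either renal rule as such.

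**Working it through.** The protocol states no figure that depends on these rules, so there is nothing to reproduce. The check is a comparison of the two texts, followed by hypothetical patients.

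**1. Side by side**

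| | Relapse rule (Patient Monitoring and Evaluation) | Flare rule (Study Drug Discontinuation, item 2) |
|---|---|---|
| Size of proteinuria rise | none stated | 30% |
| Reference value | none stated | visit 0 |
| Creatinine | not mentioned | 25% rise, and/or |
| Confirmation | two consecutive visits | repeat analysis; 24-hour ratio for proteinuria |
| What stops | study regimen (undefined) | study drug (in context, ACTHar) |
| What follows | investigator preference | prednisone |

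No sentence ranks the rules, assigns them to different periods or cross-refers them.

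**2. Hypothetical patients** (UPCR = urine protein/creatinine ratio)

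- UPCR 2.0 at visit 0, then 2.2 and 2.4: 2.2/2.0 = 1.10 and 2.4/2.0 = 1.20. Both are rises, and both are below 1.30. Relapse rule met; flare rule not met.
- UPCR 2.0, 1.8, 1.6 with creatinine 1.0 rising to a confirmed 1.3: 1.3/1.0 = 1.30, above 1.25, while proteinuria falls. Flare rule met; relapse rule not met.
- UPCR 3.0, then 4.0 and 4.2: 4.0/3.0 = 1.33 and 4.2/3.0 = 1.40. The relapse rule is met, and so is the flare rule once the rise is confirmed on a 24-hour collection.
- UPCR 3.0, 0.4, 0.6, 0.9: the last two values rise on the visit before but stay below visit 0. The relapse rule is met or not depending on its unstated reference; the flare rule is not met.

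**3. The zone of disagreement on proteinuria**

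Take the relapse rule as meaning above visit 0. The gap then runs from visit 0 to 1.30 × visit 0. At the entry limit (Inclusion Criteria, ratio above 1) this is about 1.0 to 1.0 × 1.3 = 1.3. From a starting value of 2.0 it is 2.0 to 2.0 × 1.3 = 2.6. Two consecutive values in that band stop treatment under one rule and not under the proteinuria limb of the other.

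On that reading, and if the flare is confirmed at the next visit, the 30% threshold adds no stops, because any value at or above 130% of visit 0 is already above visit 0. On other readings it does add some. For example, if the relapse rule needs a rise on each previous visit, a patient who jumps past 130% and then stays level meets only the flare rule.

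**4. What is stopped, and when**

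ACTHar lasts 3 months, or 6 if extended, out of 24: 3/24 = 12.5% or 6/24 = 25% of follow-up. If study drug means ACTHar, the flare rule has nothing to stop in the remaining 24 − 3 = 21 or 24 − 6 = 18 months. The relapse rule states no end date. If study regimen includes MMF, the relapse rule can still end MMF in that period.

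**The case against.** **The rules can both be obeyed.** The relapse sentence makes stopping mandatory, and the flare is one item in a list of reasons to stop. Nothing orders treatment to continue when a criterion is unmet. This stands. A reader might infer that the text leaves open whether either rule alone suffices, or that the rules are logically incompatible. Neither is supported: each is written as sufficient. But stopping if either is met is precisely what lets the looser rule bypass the threshold and 24-hour confirmation of the stricter one.

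**The flare text may simply quantify the relapse text.** Repeat analysis could correspond to two consecutive visits. That is possible, but it does not explain the creatinine limb, the different object of stopping or the different treatment afterwards.

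**The rules may belong to different periods.** Relapse suggests an earlier response, and the flare rule sits among ACTHar instructions. On that reading the 2.0, 2.2, 2.4 patient is not in relapse. The protocol does not say this, however, and Maintenance therapies uses both terms without distinguishing them.

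**Study regimen probably means both drugs.** Study Design describes ACTHar plus CellCept. The Statistical/Analytical Plan speaks of serious adverse events in the study regimen. The relapse sentence changes term immediately after a sentence that names ACTHar alone. This largely stands, so it would be too strong to call the term evenly ambiguous. The planned 2 years of MMF is not itself in conflict with a stopping rule. What remains is that the term is undefined and that the two rules then stop different things.

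**Classification is partly covered.** Where a flare leads to a glucocorticoid increase, the non-responder sentence plausibly applies. A relapse managed without steroids is clearly left open.

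**Conclusion.** The point holds as an inconsistency of wording that should be fixed. The two renal rules differ in size, reference value, creatinine criterion, confirmation, what follows and, on the natural reading, what is stopped. Confidence is high for the mismatch itself. It is lower for the meaning of the two terms: that study drug means ACTHar and study regimen means ACTHar plus MMF is inferred from context.

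The size that can be stated is the band from visit 0 to 130% of visit 0, assuming visit 0 is the relapse reference. Two stronger inferences are not supported:

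- **A frequency, or an effect on the primary result.** The documents give no within-patient variability for proteinuria. The urine times in the Biomarkers section (day 0, weeks 4, 12 and 24) are for biomarkers, and the attached visit schedule is not in the text available. Any simulated rate would reflect its assumptions. With 10 patients per arm, one reclassified patient moves an arm's response rate by 1/10 = 10 percentage points, but that is only the unit of measurement, not an estimate.
- **Bias because the trial is open-label.** Both arms receive ACTHar, on the same schedule after the first month, and the analysis centres on comparison with historical rates of 20% and 50%. No mechanism acting differently between arms is shown.

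**What to change.** The sponsor should reconcile Patient Monitoring and Evaluation with Study Drug Discontinuation, item 2, and align the discretionary prednisone switch in Treatment Description with the result. The amended text should do three things:

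1. Make the renal discontinuation criteria agree, including the reference value and the confirmation step, or state that relapse and flare are separate events and when each applies.
2. Define study regimen and study drug, so that it is clear whether ACTHar alone, or ACTHar and MMF, is stopped.
3. State whether patients stopped under either rule count as non-responders.

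No view is given on which criterion or which treatment rule is right. The cost is a protocol wording amendment, with no extra patients, visits or tests.
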